Overall Study Protocol: 150 systolic HF patients will each undergo an initial clinical and mechanism-oriented assessment battery (involving 2-3 visits, depending on the site where they are enrolled) before and after being enrolled into one of 3 exercise training arms. The pre-/post- evaluations will include 1. a battery of physical function (aerobic and strength) evaluations, 2. serology, 3. muscle biopsy, and 4. DXA scan. The study population will be randomized into one of three 12-week exercise training arms (aerobic, combined aerobic-strength, and inspiratory muscle training [IMT]).

A SAS program will be written to randomly allocate patients to the exercise training arms (see statistics below), also balancing gender and statin-use (90) among these 3 exercise training groups. Enrollment into the exercise training groups will be on a rolling admission.

Notably, we used a 2-3 visit comprehensive assessment protocol as part of our pilot study. It was well tolerated by subjects with no complaints of excessive fatigue or inconvenience. We provided a gap of at least 15 minutes between each of the subparts, with leeway to allow extra time if that is requested by the subject or if it seemed indicated to the study staff. Furthermore, visits were arranged such that assessments requiring physical exertion were alternated with those which are physically non-taxing (e.g., questionnaires done at rest) to help

ensure that the overall protocol was well-tolerated. Heart rate and relative perceived exertion were also checked prior to each subpart of the assessment to confirm that the subject's baseline parameters had been restored before testing proceeded.

Exercise training will be 3X/week, for 60 minutes, over 12 weeks for each of the 3 exercise regimens through a combination of on-site and home-based exercise sessions. Phone calls will be completed weekly by trained exercise based research staff to check in with study patients, work to overcome barriers and modify exercise regimens. Each participant will exercise for a maximum of 12 weeks. If subjects miss training sessions due to intercurrent illness, travel or other reasons, the duration will not be extended as the proposed trial is based on an 'intention to treat' model.

The comprehensive 2-3-visit evaluation (including physical function plus muscle biopsy, and DXA) will be repeated at the end of the exercise training period.

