mRNA levels will be determined by real-time PCR using the Applied Biosystems® StepOne real-time PCR analyzer. Multiplexed amplification reactions will be performed using GAPDH as an endogenous control (GAPDH primers/VIC-labeled) using the TaqMan One Step PCR Master Mix reagents Kit (#4309169, Applied Biosystems). Probes/primers for the specific genes to be analyzed will be purchased directly from Applied Biosystems. The following amplification settings will be used: Stage 1 (reverse transcription): 48°C for 30 min; Stage 2 (denaturation): 95°C for 10 min and Stage 3 (PCR): 95°C for 15 sec and 60°C for 60 sec for 40 cycles. The Ct (Threshold cycle) values for each reaction will be transferred to a Microsoft Excel spreadsheet and calculation of relative gene expression will be performed from this data according to published algorithms (TaqMan Cytokine Gene Expression Plate 1 protocol, Applied Biosystems). All RNA samples will be analyzed in triplicate, with the mean value used in subsequent analyses.

Of note, in our pilot studies, biopsy data was initially evaluated on different 96-well plates to allow biopsy processing before the completion of the study; however, this was associated with high variability and poor precision. Analyses were then repeated with all of the biopsy samples on the same plate. This technique strengthened our analysis and revealed key differences and correlations between gene expression and function. In this proposed study, we shall prepare and store cDNA from the muscle biopsies in small groups as the biopsies are performed, and then perform rtPCR analyses batched by exercise arm in order to minimize plate-to-plate variation in the rtPCR data.

- **Microscopic Analyses:** [name] and a consulting microscopy technician will complete all light microscopic analyses at the Boston VA. [name] has an extensive track record of skeletal muscle phenotypic analysis. Both he and his laboratory staff will work directly with [name] to ensure the phenotypic assessments are completed in the most useful fashion. Given the controversial perspectives regarding the effects of disease vs.

deconditioning on skeletal muscle physiology and function, the attention to phenotypic assessments will be prioritized as a vital perspective relative to gene expression patterns and serologic assessments of inflammation.

- Muscle Tissue Histology and Morphometric Assessments

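### rtPCR plates are batched by exercise arm, with no rule that a patient's two biopsies share a plate or that change is taken on the log scale, so plate variation can reach the Aim 2 regimen comparison

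*Combined protocol and SAP*

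**What the plan says.** Under Skeletal Muscle Analyses (mRNA extraction and rtPCR), the plan reports that in the pilot "biopsy data was initially evaluated on different 96-well plates". The sponsor's own judgement of that layout is unfavourable: "however, this was associated with high variability and poor precision". The remedy was a complete rerun, which the sponsor credits with strengthening the results: "Analyses were then repeated with all of the biopsy samples on the same plate".

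For this trial the laboratory will "perform rtPCR analyses batched by exercise arm in order to minimize plate-to-plate variation in the rtPCR data". Ahead of that step, material is stored as it is collected; staff will "prepare and store cDNA from the muscle biopsies in small groups as the biopsies are performed". GAPDH is amplified in the same reaction as an endogenous control. "All RNA samples will be analyzed in triplicate, with the mean value used in subsequent analyses". On the scale of the result, the plan says only that "calculation of relative gene expression will be performed from this data according to published algorithms", citing a manufacturer's protocol. Under Overall Study Protocol, "Enrollment into the exercise training groups will be on a rolling admission".

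Aim 2 in the statistics section uses change in expression from baseline to post-training. It first treats that change as a predictor of functional change. It then compares it between regimens with and without direct skeletal muscle stimulation. General considerations says that outcomes will be checked against regression assumptions and transformed if needed. It adds that isolated significant associations will not be given undue weight.

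The text available for review does not require a patient's two samples to be run on one plate. It names no inter-plate calibrator, plate term or log scale for change in expression.

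**The concern.** Plate is a nuisance factor that the sponsor has already seen do damage. For a comparison between arms, the usual protection is to spread every arm over every plate. Batching by arm does the opposite: each plate belongs to one arm, so whatever plate difference remains after GAPDH normalisation lines up with the exposure.

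Aim 2 analyses within-patient change, so harm is not automatic. A plate shift that is additive on the log scale cancels when both samples of a patient sit on one plate and change is taken as a difference of logs. If pairs are split, the shift stays in the change score. If pairs are kept together but raw relative expression is subtracted, the plate factor multiplies any true change that the arms have in common. The plan leaves both points open.

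At stake is the comparison of regimens with and without direct muscle stimulation, which could lose precision or gain false positives. If no plate holds both visits, plate and visit cannot be separated within an arm, and no plate term added later can repair that.

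**Working it through.** The plan gives no figure for plate variation, so there is none to reproduce. The check counts plates, sets the scale from the pilot, and then works out what each permitted layout does.

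**Plates needed.** Wells per gene = patients × 2 biopsies × 3 replicates.
- 150 enrolled (Table 5): 150 × 6 = 900 wells; 900/96 = 9.4, so 10 plates.
- 120 evaluable after 20% attrition: 120 × 6 = 720 wells; 720/96 = 7.5, so 8 plates.
- By arm, 48 aerobic and 48 IMT patients need 288 wells each (3 plates), and 24 combined need 144 wells (2 plates): 3 + 3 + 2 = 8.

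One plate per arm is therefore impossible at 96 wells. That format is the pilot's; this trial's is not stated. With 48 wells the count is 15 to 19 plates, with 384 wells 2 to 3. Sample size/Power gives 210 patients rather than 150; that would need 1,260 wells, or 14 plates of 96.

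**Sample SD.** From the heart-failure means and SDs in Preliminary Data, Phase II, natural-log SD = √ln(1 + (SD/mean)²). For FoxO3, √ln(1 + (4.3/6.5)²) = 0.60. The others are UBB 0.46, PSMA1 0.43, FoxO1 0.69 and GLUL 0.85. A value of 0.5 is used below.

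**Assumptions not in the documents.** Plate SD s after GAPDH is 0.05, 0.1, 0.2, 0.35 or 0.5 natural-log units. Pre and post sample errors are independent. A plate holds 32 samples. The contrast is IMT (48) against aerobic plus combined (72), which is my reading of the two categories. There is no true difference between arms, and the nominal level is two-sided 5%.

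**No plate effect.** Variance of one change = 2 × 0.5² = 0.5. V0 = 0.5 × (1/48 + 1/72) = 0.01736, so SE = 0.132.

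**Results by layout, plates batched by arm.** Loss = 1 − V0/V, read as the share of patients effectively lost.

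| Layout | False-positive rate at s = 0.05 / 0.1 / 0.2 / 0.35 / 0.5 | Loss |
|---|---|---|
| 1. Pairs on one plate, log change | 5% throughout | none |
| 2a. Pairs on one plate, raw change, no common shift | 5% throughout | – |
| 2b. As 2a, common shift 0.2 log | 5 / 5 / 6 / 6 / 7% | – |
| 2c. As 2a, common shift 0.5 log | 5 / 6 / 7 / 12 / 17% | – |
| 3. Samples at random within arm, log change | about 5% | 0.6 / 2.5 / 9 / 24 / 39% |
| 4. Plates filled in order of collection, log change | 5 / 5 / 7 / 9 / 13% | 1 / 4 / 14 / 34 / 51% |
| 5. All pre samples, then all post, log change | 7 / 13 / 31 / 49 / 58% | – |

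The rates come from simulation: 20,000 runs per setting for layouts 4 and 5, and 4,000 for the others. Layout 4 assumes even entry over 104 weeks and 13 weeks between biopsies, which splits 24.5% of pairs. Entry over 78 weeks splits 32% and gives 5 / 5 / 7 / 12 / 17%. Entry over 130 weeks splits 20% and gives 4 / 5 / 6 / 8 / 10%. Layout 5 uses 8 plates, so some plates hold both visits. With 10 plates and none holding both visits, the rates are 8 / 16 / 37 / 55 / 63%.

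**Hand check of layout 3 at s = 0.2.** In an arm of 96 samples on 3 plates, the chance that a pair is split is 1 − 31/95 = 0.674. In the combined arm (plates of 32 and 16) it is 1 − (32×31 + 16×15)/(48×47) = 0.454. The average over the 72 is (48×0.674 + 24×0.454)/72 = 0.600. V = (0.5 + 0.08×0.674)/48 + (0.5 + 0.08×0.600)/72 = 0.01915, so SE = 0.138 and the loss is 1 − 0.01736/0.01915 = 9%.

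**Hand check of the 10-plate variant at s = 0.2.** The squared plate weights sum to (32² + 16²)/48² = 0.556 for IMT and (32² + 16² + 24²)/72² = 0.358 for the rest.
- Plate variance of the contrast = 2 × 0.04 × (0.556 + 0.358) = 0.0731.
- True variance = 0.01736 + 0.0731 = 0.0904.
- Variance that the test estimates = (0.5 + 0.08×0.444)/48 + (0.5 + 0.08×0.642)/72 = 0.0188.
- Rate = 2[1 − Φ(1.96 × √(0.0188/0.0904))] = 37%, as simulated.

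**Different assumptions.** A second set of runs used pre-post correlation 0.5, the FoxO3 spread (0.87 on the log2 scale) and plate SD 0.25 / 0.5 / 1.0 Ct.
- Paired, log change: 5.4 / 5.3 / 5.1%.
- Paired, raw change, common shift of 0.5 log2: 6.4 / 8.1 / 16.3%.
- Pre and post on separate plates, log change: 39 / 60 / 72%.

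The direction is the same.

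**Pairs on one plate with arms mixed.** About 5% on the log scale, 4.1 to 5.5% on the raw scale with a common shift of 0, 0.2 or 0.5, and no loss of precision.

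**The case against.** The strongest reply is that the plan is silent rather than wrong. Both samples of a patient belong to the same arm, so batching by arm keeps pairs in one batch, and storing cDNA first makes pairing easy. Layouts 4 and 5 are described nowhere, and the largest rates come from layout 5. The plate SD is assumed, and at 0.2 or below every layout except layout 5 stays at 7% or less. GAPDH in the same well is a real safeguard. The cited manufacturer's protocol may use a calibrator or yield log values; that cannot be checked here. With pairs kept together, the raw scale does little harm unless expression shifts substantially in every arm. Finally, the contrast is the second analysis of Aim 2, and the plan already discounts isolated findings.

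Much of this stands. It makes the harm conditional and limits its weight. Using the project timeline for entry, or a larger sample SD, also lowers the layout 4 rates, by one or two points in most settings and four at most.

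Three things remain. Batching by arm permits pairing without requiring it. GAPDH cannot remove gene-specific plate effects, and triplicates averaged on one plate do not reduce plate variation. Discounting isolated results also helps less when one layout is used for every gene, because several genes can be disturbed together. Mixing arms is not superfluous either: it removes the raw-scale inflation of up to 17% that batching by arm leaves even with pairs on one plate.

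**Conclusion.** The concern holds. The plan states an allocation rule that aligns plate with the exposure, after the sponsor itself found plate variation troublesome, and it leaves open the two conditions that would make the rule harmless.

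The likely size is modest. With both conditions met there is no effect. With plates filled in order of collection, the false-positive rate is 5% to 13% and the precision loss 1% to 51% over the assumed plate SDs. Splitting pairs is the larger risk; the raw scale matters mainly when all arms shift together. Rates of 31% or more need layout 5 or its 10-plate variant and a plate SD of at least 0.2, and should be read as a bound.

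These sizes rest on the assumed plate SD, 96-well plates, 48/24/48 evaluable patients and IMT against the rest. The direction does not depend on the plate SD. The point should be fixed; confidence is medium because the deciding SD is unknown.

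**What to change.** Replace the rule of batching by arm with text such as: *Each patient's pre and post samples are run on the same plate. Patients are assigned to plates at random, with the arms mixed on every plate. Samples are coded so that the laboratory is masked to arm. Change in expression is analysed on the log (delta-Ct) scale.*

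Pairing and the log scale are the essential part. Mixing arms protects the comparison if the plate shift is not additive on that scale.

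For 120 evaluable patients, 8 plates of 15 work: 6 aerobic, 6 IMT and 3 combined, with 2 or 3 of each 6 from Boston. Each plate uses 15 × 6 = 90 of 96 wells and leaves 6 for controls. A plate factor is optional, because an additive shift cancels within pairs. With this map it costs no precision: the variance of combined against aerobic stays at 1/24 + 1/48 = 0.0625 times the variance of a single change.

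The cost is small. Both schemes need 8 plates per gene, with no extra samples or procedures. The work is a new plate map, sample coding, and holding stored cDNA until samples from all arms are available. The plan already stores cDNA before rtPCR.

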Phenotype and Metabolism: Phenotypic and metabolic changes in peripheral skeletal muscle of HF patients are well described (3,4,17-19). Phenotypic changes in fiber composition include reduced type I oxidative fibers (slow twitch) with increases in anaerobic type II (fast twitch) or hybrid fibers. Histomorphometric analyses also demonstrate decreased fiber sizes as well as reduced number and altered structure of mitochondria. Even though there is an increase in skeletal muscle fibers with anaerobic, fast twitch characteristics, fiber size and cross-sectional area are dramatically reduced, leading to a significant reduction in muscle force production in HF (20).

Related studies indicate metabolism of the skeletal muscle is altered in HF with shifts in aerobic/anaerobic enzyme distribution from slow oxidative towards fast oxidative and fast glycolytic isoforms (19), decreased levels of mitochondrial creatine kinase, as well as downregulation of the sarcoplasmic reticulum Ca^{2+} -ATPase 1 (SERCA-1) (21). While some have attributed HF skeletal muscle weakening and atrophy primarily to disuse, others assert the complex skeletal muscle changes in HF constitute a disease-related myopathy (22,23) that is then compounded by the effects of muscle disuse and deconditioning (24).

HF-related changes in the diaphragm strongly support the concept of intrinsic HF myopathy. HF is associated with diaphragmatic muscle changes consistent with increased activity (25), i.e., a shift from fast to

slow myosin isoforms, an increase in oxidative capacity and decreased glycolytic activity. Nonetheless, intrinsic performance remains deficient.

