- *Aerobic training:* Originally, exercise training for HF was predominantly oriented toward aerobic training modalities, building on the rationale that aerobic exercise stimulates healthful central cardiac responses (3,4) in adults without heart disease. Aerobic training has the potential to induce increased stroke volume and inotropy in healthy adults, as well as increased peripheral oxygen utilization. While it was generally assumed that exercise training in systolic HF patients would provide similar benefits, it was ultimately demonstrated that peripheral training effects surpass central benefits. Aerobic exercise is associated with increased skeletal muscle blood perfusion, endothelial responsiveness, healthful shifts in skeletal muscle histomorphometry, and improved mitochondrial function (oxidative capacity). Underlying these changes, improved autonomic, neurohormonal, and anti-inflammatory benefits have also been demonstrated. While it was once assumed that the potential for adverse cardiac remodeling was a risk associated with aerobic training, in fact, just the opposite occurs, probably due to decreased inflammation (62).

Overall, aerobic training provides particular benefit in relation to neurohormonal and inflammatory milieu, with improved autonomic responses, peripheral perfusion, and even remodeling benefits.

- *Strength training:* HF patients typically display substantial skeletal muscle atrophy, changes in fiber type, and associated decreases in overall strength, often presented as dyspnea and exercise intolerance (20). Reduced flexibility and balance are also associated with skeletal muscle physiological changes in HF patients. Strength training has been studied as a means to allay some of this predictable atrophic risk. In addition, increased skeletal muscle mass is a potential means to increase aerobic capacity since VO_2 becomes more efficient. Increasing strength parameters in HF patients facilitates increased functional capacity, thereby prolongs independence and improves quality of life.

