[name] brings related expertise in cellular metabolism and functional capacity in older HF patients. In one of his earliest training studies, he investigated older female HF patients participating in a resistance training trial; patients randomized to a 10-week training program had significantly increased muscle strength (increased $43.4 \pm 8.8\%$ in resistance trainers vs. $-1.7 \pm 2.8\%$ in controls, $p= 0.001$), muscle endurance (increased by $299 \pm 66\%$ vs. $1 \pm 3\%$, $p= 0.001$), and 6MWT distance (increased by 49 ± 14 m (13%) vs. -3 ± 19 m (-3%) in controls, $p = 0.03$). Most importantly, increased citrate synthase activity ($35 \pm 21\%$) was independently predictive of improved 6MWT distance ($p = 0.0024$) (8).

In a subsequent study (16 week program), HF patients (ages 67-82, mean 73 years old) in a strength training arm demonstrated increased skeletal muscle mitochondrial size, (23.4% increased size, $p< 0.015$) and associated increases in muscle strength and endurance (knee extensor and flexion), as well as increased functional capacity (peak VO₂, VAT, and 6MWT distance) (17).

While on faculty at Boston University, Boston Medical Center was selected by the NHLBI as one of HF-ACTION's (A CHF Trial Investigating Outcomes of Exercise TraiNing) 9 U-site hubs, with [name] as the U-site principal investigator (85). [name] created the infrastructure for recruitment and training into that landmark HF training trial. During the course of the 5 year trial, [name] changed professional affiliations to Brigham and Women's Hospital. Therefore, his role as principal investigator transitioned into his new affiliation, i.e., [name] had to formulate an infrastructure for this complex trial a second time. During this academic transition, [name] was commended by the HF-ACTION steering committee for excellent start-up and recruitment at the new institution.

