Standard histological techniques will be employed to analyze cross-sectional area of muscle fibers, as well as damage, inflammation, and atrophy. Histochemistry will be performed to differentiate type I from type II fibers (cytochrome C oxidase activity). Additionally immunohistochemistry using monoclonal antibodies specific to the MHC isoforms will be used to assess the hybrid skeletal muscle types. These histomorphometric and enzymatic parameters will be correlated to atrogene expression to delineate whether specific gene expression patterns translate into pertinent physiological changes, as well as changes in exercise performance.

In addition, standard measures of aerobic enzymes (citrate synthase) will be completed to establish correlations to functional parameters and associated signaling patterns. Citrate synthase will be assayed spectrophotometrically from skeletal muscle biopsies.

Serum analyses: To be completed at the same time of the muscle biopsy. A core of study nurses are available at the CSU to complete the phlebotomy required. Serum will be obtained from all individuals in this study. Standard phlebotomy technique in sterile fashion will be utilized. Whole venous blood samples will be centrifuged at the CSU for 10 min at 4C. Samples will be put into dry ice and transported to freezer storage at the JP campus. Serum will be stored at -80C until batch analyses are completed. Serum analyses will be completed at the VABHS laboratories.

Assays will be completed that are pertinent to the secondary analyses of this investigation. Insulin, CRP, IL-6, IL-1, IL-1 receptor, TNF- α , TNF α receptor, Cortisol, Adiponectin (high molecular weight and total), Glucose, electrolytes, and liver function serology will all be assessed

Dual energy x-ray absorptiometry (DXA): DXA will be completed by [name]. A GE Healthcare Lunar iDXA Bone Densitometer 5th Generation instrument with encore software version 13.6 is available for these assessments. A total body scan will be used to determine total body fat free mass and regional body composition (107). Subjects will lay flat on their back on an open table for 15 minutes while a bar passes over them. Using these DXA-based measurements, CPX performance indices will be normalized to fat free mass, thereby eliminating confounding effects of body fat. This will modify the tendency to underestimate performance among those who are overweight.

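### The type I/type II fibre split rests on an oxidative stain that training can change, and myosin typing is assigned only to hybrid fibres

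*Combined protocol and SAP*

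**What the plan says.** The section Muscle Tissue Histology and Morphometric Assessments gives two fibre-typing methods. The first makes the type I/II split: "Histochemistry will be performed to differentiate type I from type II fibers (cytochrome C oxidase activity"). The next sentence adds the second: "Additionally immunohistochemistry using monoclonal antibodies specific to the MHC isoforms will be used to assess the hybrid skeletal muscle types". The same section plans a separate oxidative measure: "Citrate synthase will be assayed spectrophotometrically from skeletal muscle biopsies". It then says that the histological and enzymatic results will be correlated with atrogene expression and exercise performance.

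The biopsy is of the vastus lateralis, before and after training: "The comprehensive 2-3-visit evaluation (including physical function plus muscle biopsy, and DXA) will be repeated at the end of the exercise training period" (Overall Study Protocol). The opening of Materials and Method lists skeletal muscle phenotype among the endpoints. Under Microscopic Analyses, phenotypic assessment is described as a priority. In the statistical section, muscle histology enters the secondary analyses under Aim 2 as a covariate.

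The plan does not say whether MHC typing covers every fibre, which method governs if the two disagree, or whether the oxidase cut-off is fixed across visits or set relative to other fibres in the same section.

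**The concern.** Cytochrome C oxidase activity reflects oxidative metabolism, whereas the type I/II distinction of interest is contractile. A classifier that can respond to the intervention is a poor basis for a before/after comparison. A type II fibre that gains oxidative activity can cross the cut-off and be counted as type I with its myosin unchanged.

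The same difficulty reaches the gene-expression analyses. The Background describes PGC-1α as driving mitochondrial biogenesis and oxidative metabolism. It is a focus gene under Skeletal Muscle Analyses and a predictor in Aim 2. A correlation between PGC-1α and oxidase-defined type I share could therefore reflect oxidative adaptation alone. Citrate synthase already captures oxidative adaptation, so what fibre typing should add is the contractile reading, and the stated method does not isolate it.

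The aerobic and combined regimens exercise the biopsied limb directly, while inspiratory training acts mainly elsewhere. Any misclassification may therefore be unequal between arms.

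**Working it through.** The plan states no figure for fibre-type proportion, so there is none to reproduce. The check has two parts.

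**1. The documents set side by side**

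- *Is oxidative the same as type I?* Background, Phenotype and Metabolism, pairs type I with oxidative and type II with anaerobic in one paragraph. The next paragraph describes a shift in enzyme distribution "from slow oxidative towards fast oxidative and fast glycolytic isoforms", so it recognises fast muscle that is oxidative. The following paragraph, on the diaphragm, lists a change in myosin isoforms and a rise in oxidative capacity as separate findings. On this account the stain separates the types imperfectly, even at baseline.
- *Does training move oxidative capacity?* The Background on aerobic training lists "healthful shifts in skeletal muscle histomorphometry, and improved mitochondrial function (oxidative capacity") among its effects. Preliminary Data, section 2, reports citrate synthase activity up 35 ± 21% in a 10-week resistance-training study, and mitochondrial size up 23.4% in the strength arm of a 16-week programme.
- *Is oxidase itself shown to change?* No. That is an inference from oxidative capacity, citrate synthase and mitochondrial size.

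**2. Illustration of size (all distribution inputs are assumptions)**

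Let log stain intensity be normal with SD s, mean 0 in type II fibres and mean log r in type I fibres. The true type I share p is the same at both visits. The cut-off is fixed at c = (log r)/2. Training multiplies activity in every fibre by g. With Φ the standard normal distribution function, the apparent type I share is

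S(g) = p·[1 − Φ((c − log r − log g)/s)] + (1 − p)·[1 − Φ((c − log g)/s)],

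and the apparent shift is S(g) − S(1).

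Worked case: p = 0.35, r = 2, s = 0.2, so c = 0.347.

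- Before (g = 1): 0.35 × 0.958 + 0.65 × 0.042 = 0.363.
- After (g = 1.2, log g = 0.182): 0.35 × 0.996 + 0.65 × 0.206 = 0.482.
- Apparent rise: 12.0 percentage points, with no fibre changing type.

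Range over p = 0.35 and 0.50, r = 1.5, 2 and 3, s = 0.2 and 0.3:

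| Rise in activity | Apparent rise in type I share (points) |
|---|---|
| 10% | 0.5 to 12 |
| 20% | 2 to 24 |
| 35% | 5 to 40 |

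The 35% row borrows the citrate synthase figure, which is for a different enzyme. The smallest shifts occur where the two populations stain very differently (r = 3), the largest where they overlap (r = 1.5).

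If fibres are instead classed relative to others in the same section, the cut-off also moves by log g. Each (c − log g) becomes (c + log g − log g) = c, so S(g) = S(1) and the shift is zero. That result needs both a relative cut-off and the same proportional rise in every fibre. The plan states neither, and a relative cut-off would not resolve fast oxidative fibres at baseline.

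**The case against.** The strongest reply is that the plan already contains the corrective data. MHC-isoform staining follows in the next sentence, a hybrid can be recognised only by staining fibres for their isoforms, and nothing forbids using those results for all fibres. Citrate synthase is assayed separately, so a rise in oxidase-defined type I share alongside raised citrate synthase and unchanged MHC would be recognisable. This stands in part: misreading is possible, not certain. It does not close the gap, because the type I/II split is assigned to the stain and the plan does not give MHC precedence.

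A reader might infer several stronger things that the documents do not support:

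- *That oxidative adaptation will be misread as a fibre-type shift.* This depends on the unstated cut-off, and the size cannot be known from the documents.
- *That inspiratory training would show no change.* The Background reports limb blood-flow and peripheral effects of this training, and item v of the Exercise Training features gives all arms warm-up and cool-down that include slow aerobic activity. The error may be differential; a zero comparator is an assumption.
- *That type-specific cross-sectional area is compromised.* The plan specifies fibre cross-sectional area without a split by type.
- *That a planned between-arm test is biased.* The statistical text available for review specifies no between-arm fibre-type comparison. Phenotype appears as an endpoint in general terms, in correlations and as a covariate.

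**Conclusion.** The concern holds in limited form. The stated type I/II classifier is an oxidative marker that the documents' own account suggests can change with training. Taken alone, a change in oxidase-defined type I share, or its correlation with PGC-1α or performance, does not identify a fibre-type shift. The direction under a fixed cut-off is clear. The magnitude is not: the illustration runs from 0.5 to 40 points across assumed inputs, and to zero under within-section classification with proportional change.

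The conclusion assumes that oxidase activity follows the oxidative changes the documents describe, and that MHC results are used as written, for hybrids. The reach is the skeletal muscle phenotype endpoint, the histology–atrogene correlations and the secondary covariates. The Aim 1 outcomes (peak VO2 and 1RM) and the sample size do not depend on it. It is worth correcting because the better method is already planned and the cost is low.

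**What to change.** In Muscle Tissue Histology and Morphometric Assessments, state that MHC-isoform immunohistochemistry defines type I, type II and hybrid for all fibres at both visits, and that this classification is the one used in the phenotype endpoint, the atrogene correlations and the secondary covariates. Keep the cytochrome C oxidase stain, but report it separately as an oxidative-capacity measure alongside citrate synthase, and state whether its cut-off is fixed or relative.

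The antibodies and the OCT-embedded frozen fragment are already in the plan, so no new tissue or assay is needed. The cost is the reading time to score all fibres on the MHC sections rather than hybrids alone, plus a short change of wording.
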